3.13. Rescue Medications, Treatments, and Procedures

The Investigator will determine the appropriateness and use of any medications, treatments, or procedures required to adequately treat study-related toxicities or complications (e.g., treatment of drug-induced nausea or vomiting, treatment of myelosuppression or anemia). Any rescue medication, treatments, or procedures will be consistent with accepted medical practice and institutional guidelines.

3.14. Prohibited Cancer Treatments

The following medications/therapies intended to treat the patients' underlying cancer are prohibited during the study

- Other investigational agents
- Other cancer therapies other than those which the patient has received for at least 6 months and which the Investigator, Medical Monitor, and Sponsor representative agree are unlikely to interfere with the study objectives (e.g., hormonal therapy for prostate cancer)

3.15. Discontinuation of VRx-3996/Valganciclovir

VRx-3996/valganciclovir may be discontinued in the event of any of the following:

- Clinically significant progressive disease (sites may elect to allow patients to continue study drug administration and confirm progressive disease with a follow-up evaluation to rule out pseudoprogression as outlined in the RECIL criteria)²³
- Unacceptable AE(s) considered secondary to VRx-3996/valganciclovir despite appropriate therapy
- Withdrawal of consent for study drug administration by the patient (patient may agree to continue to be followed for safety and survival)
- Noncompliance by the patient at the discretion of the Investigator and Medical Monitor with agreement by the Sponsor representative

- Termination of study by the Sponsor

If the patient withdraws consent for treatment, it is important to continue to collect follow-up data, if possible. The Investigator must discuss this option with the patient.

3.16. Restarting Study Drugs at Relapse

Patients who experienced clinical benefit while on study treatment, and then experience progressive disease while not receiving VRx-3996/valganciclovir, may have study drugs restarted if the following conditions are met:

- Restarting study drugs is considered in the patient's best interest by the Investigator
- The patient has not developed any contraindications to either study drug
- The Investigator has discussed restarting study drugs with the study Medical Monitor who agrees that restarting of study drugs is appropriate
- The study has not been closed by the Sponsor

Patients will generally restart study drugs at the RP2D; however, the dose and schedule may be altered if considered in the best interest of the patient by the Investigator, Medical Monitor, and Sponsor representative.

3.17. Removal of Patients from Study Follow-Up

No additional follow-up of a patient will occur in the event of any of the following:

- Request by the patient to no longer be followed (e.g., withdrawal of consent for follow-up)
- Patient is lost to follow-up
- Termination of study by Sponsor

3.18. Replacement of Patients During Phase 2 Portion of Study

Patients who are unable to complete at least 1 disease assessment to evaluate efficacy during the Phase 2 portion of the study may be replaced.

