3.2. Phase 2 (Dose Expansion)

3.2.1. Phase 2 Sample Size

The Phase 2 portion of the study will accrue 30 patients. Any patients in screening at the time that the 30th patient is enrolled will be permitted to enroll, should they be eligible. This sample size is based on a Simon's 2-stage design where the Phase 2 portion of the study may be stopped if none of the first 10 treated patients have a response. The hypothesized response rate of a poor drug is 5%, while the hypothesized response rate of a good drug would be at least 20%. Using a 1-sided alpha of 0.05 and power of 80%, if at least 1 of the first 10 patients has a response, the Simon's design recommends accruing up to at least 29 total subjects to test the null hypothesis. The probability of stopping early is 59.9% with a type I error rate of 0.0468 (<http://cancer.unc.edu/biostatistics/program/ivanova/SimonsTwoStageDesign.aspx>).

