Disease assessment – Performed at least every 2 cycles with initial assessment after Cycle 2 (may be adjusted based on Investigator discretion following discussion with Medical Monitor). Disease assessment performed using a modality appropriate for the patient's tumor (e.g., PET-CT scan, CT scans, MRI). Use a consistent modality for the same patient throughout the study. May include assessment of bone marrow (e.g., aspirate, biopsy) with cytogenetics and/or fluorescence in situ hybridization (FISH) as indicated. Disease assessment data including actual scan data and radiology reports will be submitted to the Sponsor as it becomes available for evaluation by a central radiologist reader. Investigator assessment of clinical response will be documented in the source and in Electronic Data Capture. When available, tumor tissue collected during the study should be provided to the central pathology lab.

PK sample(s) – [Blood] Collected for both valganciclovir and VRx-3996. Timepoints per [Section 6.4.1](#). Collection procedure outlined in the Study Manual for all sites. Study visits with PK assessments should occur on days that the patient will take both study drugs, VRx-3996 and valganciclovir.

Urine PK collections – At selected sites only urine will be collected for levels of VRx-3996 and its metabolites on Cycle 1 Day 1. Patients will be instructed to void urine prior to administration of study drug, then all urine will be collected as described in [Table 14](#) depending on the patient Cohort. Detailed instructions are included in the Study Manual.

Hepatitis B antigen/antibodies – [Blood] Includes surface antigen, core antibody, and surface antibody. Collection procedure outlined in the Study Manual.

Hepatitis B DNA PCR – [Blood] Collected on patients with positive hepatitis B core Ab or surface Ag.

Hepatitis C antibodies – [Blood] Collection procedure outlined in Study Manual. Any patient positive for hepatitis C Ab will be evaluated for hepatitis C circulating virus by qPCR.

Hepatitis C qPCR – [Blood] Required only for patients with evidence of hepatitis C based on serology.

Human leukocyte antigen (HLA) testing – [Blood] Determination of HLA class I and II. Collection procedure outlined in the Study Manual.

Exploratory biomarkers:

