3.1.2 Phase 2 (Dose Expansion)

The phase 2 dose expansion portion of the study will evaluate the RP2D in 30 patients with relapsed/refractory EBV⁺ lymphomas. This sample size is based on a Simon's 2-stage design where the Phase 2 portion of the study may be stopped if none of the first 10 treated patients have a response.

The dose and schedule of nanatinostat and valganciclovir used during the Phase 2 portion of the study will be the RP2D for nanatinostat and valganciclovir as determined by the SRC at the conclusion of the Phase 1b portion of the study. A Core SRC consisting of 2 investigators and 1 clinical expert appointed by the Sponsor will assess the toxicity during the phase 2 dose expansion and modify the dosing schedule of nanatinostat and/or valganciclovir as appropriate. Changes to the schedule will be enacted with minimal or no change to the total daily dose. Patients who are unable to complete at least one disease assessment to evaluate efficacy during the Phase 2 portion of the study may be replaced.

In both phases, patients will continue to receive nanatinostat/valganciclovir if, in the opinion of the Investigator, the patient is still receiving clinical benefit, the patient does not demonstrate progressive disease (in the absence of clinical deterioration, patients may continue on study drug until a repeat scan confirms progression), and in the absence of unacceptable toxicity.

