4.8 Determination of Sample Size

The Phase 2 portion of the study will accrue 30 patients. Any patients in screening at the time that the 30th patient is enrolled will be permitted to enroll, should they be eligible. This sample size is based on a Simon's 2-stage design where the Phase 2 portion of the study may be stopped if none of the first 10 treated patients have a response. The hypothesized response rate of a poor drug is 5%, while the hypothesized response rate of a good drug would be at least 20%. Using a 1-sided alpha of 0.05 and power of 80%, if at least 1 of the first 10 patients has a response, the Simon's design recommends accruing up to at least 29 total patients to test the null hypothesis. The probability of stopping early is 59.9% with a type I error rate of 0.0468.

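### Phase 2 replacement leaves the Simon count undefined; if the 5% null rate is per treated patient and unscanned non-responders are replaced, the stated type I error of 0.0468 does not hold

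*Protocol*

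**What the plan says.** Protocol 3.2.1 sizes Phase 2 by a Simon two-stage design with a poor-drug response rate of 5%, a good-drug rate of at least 20%, one-sided alpha 0.05 and 80% power. Phase 2 may be stopped if "none of the first 10 treated patients have a response"; otherwise accrual goes on to at least 29, with 30 planned. SAP 4.8 repeats this and states: "The probability of stopping early is 59.9% with a type I error rate of 0.0468". Neither document prints the final cut-off or says whether the 5% and 20% are rates per treated or per assessed patient.

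Protocol 3.18 adds: "Patients who are unable to complete at least 1 disease assessment to evaluate efficacy during the Phase 2 portion of the study may be replaced". SAP 3.1.2 likewise says that patients "unable to complete at least one disease assessment to evaluate efficacy during the Phase 2 portion of the study may be replaced". Neither restricts the reason or says whether the replaced patient stays in the Simon count. By contrast, the Phase 1b rule (Protocol 3.1.9) limits replacement to reasons other than drug-related toxicity.

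On timing, Section 7 of the protocol says of disease assessment: "Performed at least every 2 cycles with initial assessment after Cycle 2". With 28-day cycles that is about 8 weeks.

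On the analysis population, the protocol's efficacy dataset (12.1) and the SAP's Efficacy Evaluable Set (4.2) both require a post-baseline tumor assessment, and SAP 4.6.1 bases all efficacy summaries on that set. SAP 4.6.5.2, however, counts non-evaluable patients as non-responders and keeps them in the denominator.

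**The concern.** A Simon design has its quoted error rates only if the patients counted at each look are fixed without regard to outcome. Here a patient with no scan cannot be recorded as a responder but can be exchanged for a new patient who can. Some of those without a scan in the first 8 weeks will be early deaths or rapid decliners, since the population is relapsed/refractory and Protocol 1.11 calls these malignancies often aggressive. If such patients leave the count, early failures stop weighing against the regimen, and more patients can contribute a response while the cut-off stays the same. At stake are the futility look, which Protocol 3.20 relies on to limit how many patients are exposed, the type I error quoted in both documents, and the reported response rate.

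**Working it through.** **Inputs.** p0 = 0.05, p1 = 0.20, stage 1 stops at 0 of 10, total 29 (Protocol 3.2.1, SAP 4.8). The final cut-off is not printed and is recovered in step 1. The no-scan share d is not in the documents; it is assumed and varied from 5% to 30%.

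**1. Reproduce the stated design.** With response probability p per counted patient:

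- P(early stop) = (1 − p)^10
- P(pass) = Σ over x = 1 to 10 of Bin(x; 10, p) × P(Y ≥ 4 − x), with Y ~ Bin(19, p)

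At p = 0.05, early stopping is 0.95^10 = 0.599. The pass probability is 0.3151 × 0.0665 (x = 1) + 0.0746 × 0.2453 (x = 2) + 0.0105 × 0.6226 (x = 3) + 0.0010 (x ≥ 4) = 0.0210 + 0.0183 + 0.0065 + 0.0010 = 0.0468. At p = 0.20 it is 0.8011. So 0/10, then at least 4/29, reproduces the stated 59.9%, 0.0468 and 80% power. With 29 patients, a cut-off of at least 3 gives 0.1353, and at least 5 gives 0.0124 with power 0.681.

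**2. Add replacement.** Suppose the 5% is per treated patient, a share d has no scan, none of these responds, and all are replaced. The rate per assessed patient is then q = 0.05/(1 − d). Two counting rules are possible.

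- *A: both stages counted on assessed patients.* Use the step 1 formulas with p = q.
- *B: stage 1 on the first 10 treated, as written; final count on 29 assessed.* Let k ~ Bin(10, 1 − d) be the number assessed among the first 10. P(pass) = Σ over k of Bin(k; 10, 1 − d) × Σ over x ≥ 1 of Bin(x; k, q) × P(Y ≥ 4 − x), with Y ~ Bin(29 − k, q). Early stopping stays at 0.95^10.

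| d | q | A: type I | A: early stop | B: type I | B: early stop |
|---|---|---|---|---|---|
| 0 | 0.0500 | 0.0468 | 59.9% | 0.0468 | 59.9% |
| 5% | 0.0526 | 0.0546 | 58.2% | 0.0534 | 59.9% |
| 10% | 0.0556 | 0.0641 | 56.5% | 0.0610 | 59.9% |
| 20% | 0.0625 | 0.0898 | 52.4% | 0.0805 | 59.9% |
| 30% | 0.0714 | 0.1291 | 47.7% | 0.1075 | 59.9% |

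**3. Readings under which nothing changes.** If the first 10 and first 29 treated patients are counted, with unscanned patients as non-responders, p stays at 0.05 and both stated figures hold. They also hold if 5% and 20% are rates per assessed patient and both stages are counted on assessed patients.

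**4. Effect on the reported response rate.** Restricting the denominator to assessed patients multiplies the per-treated rate by 1/(1 − d). At d = 20%, 5% becomes 0.05/0.8 = 6.25% and 20% becomes 0.20/0.8 = 25%. This bias comes from the efficacy set and is present with or without replacement.

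**The case against.** The strongest reply is that the documents never say the Simon rule counts only scanned patients. Stage 1 is written on treated patients, replacement is optional, and SAP 4.6.5.2 already treats non-evaluable patients as non-responders. A reader might infer that both the 0.0468 and the 59.9% fail outright. The text does not support that: the 59.9% moves only under rule A, which contradicts the first-stage wording, and both figures survive under the readings in step 3. This part of the objection stands.

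It does not close the point. SAP 4.6.5.2 conflicts with SAP 4.6.1 and concerns the response-rate denominator, not who fills the Simon places. Under rule B with d = 10%, about 29/0.9 = 32.2 patients are treated to obtain 29 assessed while the cut-off stays at 4. Keeping all of them in the response-rate denominator would not restore 0.0468.

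A reader might also infer that replaced patients are almost all treatment failures. The documents do not show this. The Schedule of Events lists a disease assessment at End of Treatment (a table note qualifies that visit's assessments as if needed), and Protocol 6.3.1 asks for an attempt to bring back patients who stop off schedule. Some early progressors would therefore be assessed and not be replaceable, and the unassessed also include withdrawals and losses to follow-up. Nor can a no-scan share be taken from the arginine butyrate study in Protocol 1.5: 11 of its 15 patients received at least 28 days of treatment, but all 15 were evaluable for response.

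Finally, SAP 4.6.5.5 plans no hypothesis test and the stopping rule is permissive. That limits the consequence, but both documents still quote a type I error and rely on a futility look, and these need a defined count.

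**Conclusion.** The point holds in a limited form. The documents leave the Simon count undefined once patients are replaced. If the null rate is per treated patient and unscanned non-responders are replaced, the type I error is above 0.0468 and already passes 0.05 at a 5% no-scan share, reaching 0.061–0.064 at 10% and 0.080–0.090 at 20%. These sizes rest on an assumed share, on full replacement, on no responders among those replaced, and on the recovered cut-off of 4 in 29; with less replacement the inflation is smaller. With no formal test planned, the practical effect is on the futility look, the accuracy of the quoted error rate and an upward-biased response rate, not on a confirmatory claim. It should be corrected because the remedy is simple.

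**What to change.** In Protocol 3.2.1 and 3.18 and SAP 3.1.2 and 4.8, state that the Simon counts are the first 10 and the first 29 patients dosed in Phase 2, in order of first dose, and that a patient with no post-baseline disease assessment is a non-responder at both looks. Print the final cut-off (at least 4 of 29, if that is what was intended). Keep that count at 29 although 30 are planned: at least 4 of 30 gives 0.0513 even without replacement.

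Replacement need not be deleted. Replacement patients may be enrolled for descriptive or PK purposes, provided they do not take a place in either count that belongs to a treated patient without a scan. Reconcile SAP 4.6.1 with 4.6.5.2 so that the reported response rate also keeps treated, unassessed patients in the denominator.

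The cost is a short text change in each document and no extra patients. The stated 0.0468 and 59.9% then apply, as does the 80% power for a 20% rate per treated patient. The observed response rate may be slightly lower.

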3.19. Handling of Patient Withdrawal or Termination

Data generated from patients prior to withdrawal from the study will be maintained and utilized in the final study analysis. No data generated from patients after their withdrawal from the study will be collected.

3.20. Premature Termination or Suspension of Study

In the event that the Sponsor elects to terminate or suspend this study prior to completion, the Sponsor will discuss the feasibility of continued administration of VRx-3996/valganciclovir with each participating Investigator for those patients that appear to be benefitting from VRx-3996/valganciclovir.

The Sponsor will also cooperate with participating sites in terms of collecting outstanding study data sufficiently to allow for the generation of a study manuscript.

In the interest of avoiding the administration of VRx-3996 to more patients than is reasonable in the dose expansion phase of the study, this study will utilize a Simon's 2-stage design.²⁵ See [Section 3.2.1](#) for sample size details and stopping rules of the Simon's 2-stage design.

4. STUDY ELIGIBILITY

4.1. Inclusion Criteria

1. Signed, informed consent
2. Age 18 or more years
3. ECOG PS²⁶ of 0 to 2 or Karnofsky Performance scale (KPS) $\geq 60\%$
4. Failed any available standard therapy with a reasonable likelihood of clinical benefit (e.g., anti-CD20 monoclonal antibody, withdrawal of immunosuppression, cytotoxic chemotherapy)
5. Relapsed/refractory, pathologically confirmed EBV⁺ lymphoid malignancy or lymphoproliferative disease regardless of histologic subtype
6. EBV⁺ as determined by institution's usual testing method or by the Sponsor's central laboratory on a specimen that is representative of the current disease (e.g., for patients who have relapsed the biopsy specimen should have been taken post-relapse). For questions on the suitability of particular specimens, please consult the Medical Monitor
7. Absence of available therapy with reasonable likelihood of cure or significant clinical benefit
8. Evaluable [Phase 1b only] or measurable [Phase 1b and Phase 2] disease based on Recommendations for Initial Evaluation, Staging, and Response Assessment of Hodgkin and Non-Hodgkin Lymphoma: The Lugano Classification²²
9. If previously treated:
 - a. Treatment-related toxicity resolved to at least Grade 1 (alopecia excepted), or
 - b. Treatment-related toxicity resolved to at least Grade 2 with prior approval of the Medical Monitor, or
 - c. Treatment related toxicity resolved to at least the levels outlined in inclusion criterion #10, without transfusion support.
10. Adequate laboratory parameters including:
 - a. Absolute neutrophil count (ANC) $\geq 1000/\text{mm}^3$
 - b. Platelet (PLT) count $\geq 50,000/\text{mm}^3$
 - c. Hemoglobin $\geq 8.0 \text{ g/dL}$
 - d. Asparagine aminotransferase (AST)/serum glutamine oxaloacetic transaminase (SGOT), alanine aminotransferase (ALT)/serum glutamic-pyruvic transaminase (SGPT) $\leq 3.0 \times$ upper limit of normal (ULN) ($\leq 5 \times$ ULN if known liver involvement)
 - e. Total bilirubin $\leq 2.0 \times$ ULN unless considered due to Gilbert's syndrome in which case, $\leq 3.5 \times$ ULN

- f. Estimated glomerular filtration rate (eGFR) ≥ 60 mL/min/1.732 m² by Modification of Diet in Renal Disease (MDRD) equation
- g. Prothrombin time (PT) $\leq 1.5 \times$ ULN
- h. International normalized ratio (INR) $\leq 1.5 \times$ ULN
- i. Serum potassium and magnesium should be within normal limits for institution or treatment to correct out of range values should be instituted

11. Willingness to participate in collection of all required laboratory testing as defined in the protocol
12. Females must be surgically sterile, postmenopausal, or agree to use adequate contraception (adequate as determined by the judgement of the Investigator) throughout the study and for a period of 6 months after last dose of VRx-3996
13. Males must be surgically sterile or must agree to use of effective contraception throughout the study and for a period of 3 months after last dose of VRx-3996

4.2. Exclusion Criteria

1. Fewer than 14 days from prior anti-lymphoma therapy (chemotherapy, irradiation, biological, or investigational therapy), or fewer than 7 days from prior therapies if approved by the Medical Monitor. Corticosteroid treatment at doses of ≤ 20 mg/day of prednisone or its equivalent, granulocyte colony-stimulating factor (G-CSF) or granulocyte-macrophage colony-stimulating factor (GM-CSF) are permitted up to 2 weeks prior to start of study treatment.
2. Fewer than 28 days from receipt of prior HDAC inhibitor
3. Fewer than 60 days from prior hematopoietic stem cell transplantation or solid organ transplantation
4. Known primary CNS lymphoma
5. CNS metastases or leptomeningeal disease unless appropriately treated and neurologically stable for at least 4 weeks
6. Other known active cancer(s) likely to require treatment in the next year that would impact the assessment of any study endpoints
7. Refractory graft versus host disease (GvHD) not responding to treatment (e.g., steroid refractory and not responding to second-line agents)
8. Active, uncontrolled bacterial, viral, or fungal infection(s) requiring systemic therapy
9. Pregnant or currently breastfeeding
10. Positive hepatitis B core antibody or surface antigen unless quantitative DNA PCR is negative and patient will be receiving prophylaxis for reactivation
11. Positive hepatitis C viral RNA (if serology is positive for infection)
12. History of allergic reactions attributed to compounds of similar chemical or biologic composition to valganciclovir

[figure not shown]
13. Psychiatric illness/social situations that would interfere with compliance with study requirements
14. Clinically significant cardiovascular abnormalities such as uncontrolled hypertension, congestive heart failure (New York Heart Association classification \geq II), unstable angina, poorly controlled arrhythmias, or myocardial infarction within 6 months of study entry. Congenital long QT syndrome or corrected QT interval using Fridericia's method (QTcF) interval of \geq 470 msec, average of triplicate readings at screening.
15. Other severe acute or chronic medical or psychiatric conditions or laboratory abnormalities that would impart, in the judgement of the Investigator, Medical Monitor, and/or Sponsor representative, excess risk associated with study participation or would interfere with study outcome assessments
16. Known involvement of critical structures by lymphoma that is considered highly likely to result in serious outcome in the event of rapid tumor destruction
17. Known history of HHV-6 chromosomal integration (ciHHV-6)
18. Known history of HIV infection

